8.4.2.3.3 Unanticipated Problems

Unless otherwise specified above, UPs (as defined in this protocol, or as defined by the EC of record, whichever definition is more conservative) that are also AEs or SAEs, must be reported to the CSO (by REDCap, or by email and SERF if REDCap is not available) no later than when they are due to be reported to the EC.

UPnonAEs are NOT reported to the CSO but must be reported to the Clinical Trials Management (CTM) group according to their requirements and preferred methods. If the UPnonAE raises a significant potential subject safety concern, the SMM should be consulted by email or phone no later than when reports are made to the CTM.

8.4.2.3.4 Pregnancy

Unless otherwise specified above, all pregnancies will be reported (by REDCap, or by email and SERF if REDCap is not available) to the CSO no later than the first business day following the day of study personnel awareness.

Pregnancy outcome data (e.g., delivery outcome, spontaneous or elective termination of the pregnancy) will be reported to the CSO no later than the third business day following the day of study personnel awareness (by REDCap, or by email and SERF if REDCap is not available).

Pregnancy itself is not an AE. Events that meet AE or SAE criteria in relation to pregnancy, delivery, or the conceptus/neonate (see section [8.4.1](#)) are reportable (by REDCap, or by email and SERF if REDCap is not available).

In the event of pregnancy in a study subject exposed to study agent, the following actions will be taken, with the goal of ensuring maternal and fetal well-being, in consultation with the SMM, independent safety monitor (ISM), and DSMB:

- Sample collection will continue (including participation in extension visits described in Appendix C) per guidelines below:
 - Only proceed with blood draw if subject's hemoglobin value is ≥ 8.0 gm/dL (assessed via finger prick).
 - PK samples (4 mL) will be collected according to the regular study schedule (Day 1, Day 7, Day 14, Day 28, Day 56, Day 84, Day 112, Day 140 and Day 168), plus optional extension visits.
 - The finger prick used to measure hemoglobin at the visits specified above will also be used to collect blood smears for detection of Pf infection by microscopic examination, and dried blood spots for PfRT-PCR. A venipuncture (up to 0.5 mL) may also be performed if the investigators believe that a finger prick would not provide a sufficient volume of blood to prepare dried blood spots for the PfRT-PCR assay.
 - Serum storage samples will not be drawn if a subject becomes pregnant.

Abbreviated Title: Anti-malaria MAb in Mali

Version Date: October 13, 2022

- Continue to follow for safety for the duration of the pregnancy and for a period of up to 12 months (per investigator discretion) following delivery for assessment of the neonate (see Appendix D).
- Request to unblind the subject, if applicable, AND if doing so would offer a benefit to the subject.
- Report, no later than the first business day after study personnel awareness, to the ISM and DSMB.
- Advise subject to notify the obstetrician of study participation and study agent exposure, providing contact information for the obstetrician to contact the study principal investigator, should this be required, and with the subject's consent.

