1 PROTOCOL SUMMARY

1.1 SYNOPSIS

Title: Safety and Efficacy of VRC MALMAB0100-00-AB (CIS43LS), a Human Monoclonal Antibody against *Plasmodium falciparum*, in a Dose-Escalation Trial and a Randomized, Double-Blind Trial of Adults in Mali

Study Description: A two-part phase 2 trial evaluating the safety and tolerability of one-time administration of CIS43LS, as well as its protective efficacy against naturally occurring *Plasmodium falciparum* (Pf) infection over a 6-month malaria season. The primary study hypotheses are that CIS43LS will be safe and will produce protection against malaria infection. Before study agent administration, all subjects will be given artemether-lumefantrine to clear any preexisting Pf blood-stage infection.

Dose-escalation study: The first part of the study is an open-label dose-escalation study for safety and tolerability. Subjects will be assigned to 1 of 3 dose arms (N=18 total, n=6 for each dose level). Dosing will begin in the lowest dose arm. Once all subjects in that arm reach day 7 post-infusion, if no safety concerns have arisen, dosing will begin at the subsequent dose level. This process will be repeated until subjects complete the third dose arm. Subjects will be followed for safety to assess adverse events (AEs) at study visits 1, 3, 7, 14, 21, and 28 days after administration, then monthly through 24 weeks after administration. Participants who complete participation in the dose-escalation will be offered participation in extension visits to collect extra bi-weekly blood samples for pharmacokinetic (PK) analysis and to monitor for Pf infection through the end of December 2021.

After the last subject in the highest dose arm reaches day 7 safety follow-up, an interim safety evaluation will be performed before enrollment begins for the second part of the study.

Efficacy study: The second part of the study is a randomized, double-blind, placebo-controlled trial (N=330 total, n=110 for each of 3 treatment arms) to assess safety and protective efficacy of CIS43LS and placebo.

Subjects in the efficacy study will receive the study agent and be followed at study visits 1, 3, 7, 14, 21, and 28 days later, and once every 2 weeks thereafter through 24 weeks. Primary study assessments include physical examination and blood collection for identification of Pf infection and other research laboratory evaluations.

Objectives: Primary Objectives:

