1.3.2 Efficacy Study

Abbreviated Title: Anti-malaria MAb in Mali

Version Date: October 13, 2022

Study Day	Screen	Enroll ¹	0	1	3	7	14	21	28	42	56	70	84	98	112	126	140	154	168	Illness Visit	ET
Window (days)	-56 to -7	-14±7	-	+1	±1	±2	±3	±3	±3	±7	±7	±7	±7	±7	±7	±7	±7	±7	±7		
Artemether-lumefantrine administration		X ³																			
ECG	X																				
Randomization			X																		
Study agent administration			X ⁴																		
Adverse events		X	X	X	X	X	X	X	X	X	X	X	X	X	X	X	X	X	X		X
Pregnancy prevention counseling	X	X	X	X	X	X	X	X	X	X	X	X	X	X	X	X	X	X	X		X
Laboratory Evaluations																					
Test	Tube	(Blood volume in mL)																			
Urinalysis	-	X																			
Pregnancy test (urine/serum; for women)	-	X	X	X ⁵						X		X		X		X		X		X	
HIV, HBV, HCV screen ⁶	SST	3																			
CBC with differential	EDTA	3	3	3 ⁵		3	3	3													
Hemoglobin type	EDTA	(X) ⁷																			
ALT, Cr	SST	3	3	3 ⁵		3	3	3													
Blood smear and dried blood spot for Pf RT-PCR ⁸	-		X	X		X	X	X	0.5	X	0.5	X	0.5	X	0.5	X	0.5	X	0.5	X	X
PK studies	SST			8 ⁹	4		4	4		4		4		4		4		4		4	
Serum storage	SST			8			8			8				8						8	
ADA	SST			(X)			(X)			(X)				(X)						(X)	
PBMC storage	CPT			16				16												8 ¹⁰	
Daily volume (mL)	9	6	38	4	6	18	26	0.5	12	0.5	4	0.5	12	0.5	4	0.5	4	0.5	20		
Cumulative volume (mL)	9	15	53	57	63	81	107	107.5	119.5	120	124	124.5	136.5	137	141	141.5	145.5	146	166	-	-

Abbreviated Title: Anti-malaria MAb in Mali

Version Date: October 13, 2022

Study Day	Screen	Enroll ¹	0	1	3	7	14	21	28	42	56	70	84	98	112	126	140	154	168	Illness Visit	ET
Window (days)	-56 to -7	-14±7	-	+1	±1	±2	±3	±3	±3	±7	±7	±7	±7	±7	±7	±7	±7	±7	±7		

Abbreviations: ADA, anti-drug antibodies; ALT, alanine transaminase; CBC, complete blood count; CPT, cell preparation tube; Cr, creatinine; ECG, electrocardiogram; EDTA, ethylenediaminetetraacetic acid; ELISA, enzyme-linked immunosorbent assay; ET, early termination; HBV, hepatitis B virus; HCV, hepatitis C virus; HIV, human immunodeficiency virus; PBMC, peripheral blood mononuclear cell; Pf, *Plasmodium falciparum*; PK, pharmacokinetics; SST, serum-separating tube; RDT, rapid diagnostic test; RT-PCR, reverse transcription polymerase chain reaction.

(X) indicates that no additional blood will be drawn; the test will be performed from the tube shown in the preceding row.

Notes:

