9.4.4 Efficacy Analyses

The primary efficacy endpoint (efficacy study primary endpoint) is the incidence of malaria infection defined as blood smear–positive Pf infection through 24 weeks after administration. The secondary efficacy endpoint is the incidence of malaria infection as determined by RT-PCR. The efficacy analyses will be MITT.

The primary efficacy analysis will be based on time to the first infection. The survival patterns will be described by Kaplan-Meier curves for each arm and compared by the logrank test across different arms. The protective efficacy of the study product will be estimated by the hazard ratio from the Cox proportional hazards model. These analyses will be carried out by R packages that account for interval censoring: package “interval” for deriving a nonparametric maximum likelihood estimation based on the Kaplan-Meier survival curve and logrank test, and package “icenReg” for Cox proportional hazards regression. To address the heterogeneity of the study population, a Cox regression with regressors other than the study arm will be additionally performed to account for potential differences among participants. The regressors will include time of enrollment and possibly those covariates that are significantly different between the study product arms and the placebo arm in spite of randomization.

The secondary efficacy analysis will be based on the proportion of infection. The proportions of infection will be estimated for each arm and compared across arms based on Kaplan-Meier estimates along with 95% confidence intervals via R package “bpcp.” This estimation accounts

Abbreviated Title: Anti-malaria MAb in Mali

Version Date: October 13, 2022

for right censoring and the comparison should be equivalent to Fisher's exact test in case of no censoring. Though not accounting for interval censoring, the Kaplan-Meier estimates are appropriate as the interest is on infection at 24 weeks only.

The Holm method will be adopted to address the issue of multiplicity in comparing the 2 dose arms against the placebo.

The above analyses will apply to both the primary and the secondary efficacy endpoints.

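### Sections 1.3.2 and 8.4.2.3.4 do not agree on how often the malaria smear is taken from an efficacy-study subject who becomes pregnant

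*Combined protocol and SAP*

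**What the plan says.** **Efficacy schedule.** The synopsis (1.1) has efficacy subjects seen on days 1, 3, 7, 14, 21 and 28, "and once every 2 weeks thereafter through 24 weeks". In the table in 1.3.2, the row "Blood smear and dried blood spot for Pf RT-PCR" is filled at every one of these visits from day 7 to day 168. That is the window in which section 2.2.3.3 assesses protection.

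**Pregnancy.** Section 8.4.2.3.4 opens with "Sample collection will continue", subject to the guidelines that follow. The first list reads "PK samples (4 mL) will be collected according to the regular study schedule" and names days 1, 7 and 14, then "Day 28, Day 56, Day 84, Day 112, Day 140 and Day 168". The next item says "The finger prick used to measure hemoglobin at the visits specified above will also be used to collect blood smears" and adds the dried blood spots, with an optional venipuncture of up to 0.5 mL. Days 21, 42, 70, 98, 126 and 154 are not mentioned. The only collection expressly stopped is serum storage.

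**Analysis.** Pregnancy is not among the withdrawal criteria in 8.4.3. Section 9.4.4 states "The efficacy analyses will be MITT", and 9.3 defines that set as everyone randomized and dosed. Section 9 has no rule for follow-up after a pregnancy is found.

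**The concern.** The primary endpoint is smear-positive infection through 24 weeks, analyzed as time to first infection. How often a subject is sampled therefore decides which infections can be seen. If the pregnancy section is followed as it most naturally reads, a pregnant subject is smeared at half the planned frequency after day 28 and is still counted alongside subjects on the full schedule.

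The interval-censored logrank and Cox methods in 9.4.4 accommodate a wider interval around an infection that is eventually detected. They cannot recover one that appears and clears between two smears. The secondary comparison of proportions, by the plan's own account, does not allow for interval censoring. The same sentence sets the dried blood spot visits, so the RT-PCR endpoint loses the same number of samples.

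If the sponsor did intend the 14-day smears to continue, the text does not say so, and staff could follow either reading.

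**Working it through.** **1. The plan's own power figure.** Inputs from 9.2.2: 110 per arm, 10% drop-out, placebo infection rate 0.4, protective efficacy 0.5 (so 0.2 on CIS43LS), two-sided 0.025. Then n = 110 × 0.9 = 99 and z = 2.241.

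Power = Φ{[(p0 − p1) − z√(2p̄(1 − p̄)/n)] / √([p0(1 − p0) + p1(1 − p1)]/n)}

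= Φ{[0.2 − 2.241 × 0.0651] / 0.0636} = Φ(0.850) = 80.2%.

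Table 4 gives 80, so the figure reproduces.

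**2. The two schedules side by side, days 7 to 168.**

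| Source | Smear days | Number |
|---|---|---|
| 1.3.2 | 7, 14, 21, 28, 42, 56, 70, 84, 98, 112, 126, 140, 154, 168 | 14 |
| 8.4.2.3.4 | 7, 14, 28, 56, 84, 112, 140, 168 | 8 |

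After day 28 there are 10 smears at nominal 14-day gaps against 5 at nominal 28-day gaps.

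**3. Smears lost by the visit at which pregnancy is found.** Section 8.3 and the table in 1.3.2 place the post-dose pregnancy tests on days 28, 56, 84, 112, 140 and 168.

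| Found on day | Remaining smears, 1.3.2 | Remaining smears, 8.4.2.3.4 | Lost | Share of 14 |
|---|---|---|---|---|
| 28 | 10 | 5 | 5 | 36% |
| 56 | 8 | 4 | 4 | 29% |
| 84 | 6 | 3 | 3 | 21% |
| 112 | 4 | 2 | 2 | 14% |
| 140 | 2 | 1 | 1 | 7% |

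**4. Chance that a patent infection meets at least one smear.** Assume onset at random between visits, patency of D days and a gap of g days. The chance is min(1, D/g). The documents give no patency duration, so a range is shown.

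| D (days) | g = 14 | g = 28 |
|---|---|---|
| 7 | 50% | 25% |
| 14 | 100% | 50% |
| 21 | 100% | 75% |
| 28 or more | 100% | 100% |

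**5. Effect on power.** The documents give no pregnancy rate. Let a fraction f of each arm be pregnant and half of their infections be missed (the D = 14 case). Both infection rates are then multiplied by 1 − 0.5f, and the formula in step 1 is applied again.

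| f (assumed) | Power |
|---|---|
| 0 | 80.2% |
| 1% | 79.9% |
| 3% | 79.3% |
| 5% | 78.6% |
| 10% | 76.9% |

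This overstates the loss, because it treats every infection in these women as arising after the pregnancy was found. At f = 3%, the placebo arm loses about 110 × 0.03 × 0.4 × 0.5 = 0.66 infections.

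**6. Effect on the estimate.** Equal loss in both arms cancels in the ratio, so protective efficacy stays at 0.50. If 5% of one arm only were affected, apparent efficacy would be 1 − 0.2/0.39 = 0.487 (placebo only) or 1 − 0.195/0.4 = 0.513 (CIS43LS only).

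**The case against.** **The text does not cancel the other smears.** Sampling continues, only serum storage is stopped, and the listed days are introduced as PK days. The smear sentence could simply mean that no second finger prick is needed where hemoglobin is already being checked. This stands, and it makes the point an ambiguity. A reader might infer an explicit rule that 14-day smears stop in pregnancy; the documents contain none. Still, the guidelines place the smear only at the listed visits, and nothing points back to the smear row of 1.3.2.

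**The loss is smaller than a bare comparison of lists suggests.** A reader might infer that 6 of 14 smears (43%) are lost. That needs a pregnancy known before day 21. Tests must be negative before enrollment and before infusion, contraception is required from 21 days before day 0, and the next scheduled test is on day 28. Scheduled testing can therefore produce at most 5 lost smears.

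**The list was not lifted from the dose-escalation smear schedule.** A reader might suppose so because both are monthly. The dose-escalation smear row includes day 21 and has no smear on day 1 or day 7. The list instead matches the post-infusion PK row of both study parts.

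**Other routes to detection remain.** A subject infected before her pregnancy is found loses nothing. Symptomatic infection may be smeared at an illness visit. Asymptomatic infection is untreated under the national guidelines cited in 8.2.1, so it may last until the next smear. All of this stands.

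**Bias between arms is not shown.** A reader might infer bias from the possible unblinding of a pregnant subject. Unblinding is requested only where it would benefit her, smears are read centrally in Bamako, and nothing in the documents suggests that pregnancy will differ by arm.

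**The limits protect mother and fetus.** They were set with safety oversight. This is a reason to leave the hemoglobin condition alone. It does not explain the omitted smears, which can be taken by finger prick.

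**Conclusion.** The point holds as an unresolved disagreement between 1.3.2 and 8.4.2.3.4, at low severity. On the natural reading, a pregnancy found on schedule before day 168 costs between 1 and 5 of 14 smears and the same number of blood spots, while the subject remains in both efficacy analyses. What would be missed is mainly asymptomatic infection patent for less than 28 days.

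The size rests on two assumptions that the documents do not supply: the pregnancy rate and the patency duration. For 1% to 5% pregnant with half of their infections missed, power is 79.9% to 78.6% against 80.2%. If patency is 28 days or more, nothing is lost at these nominal gaps. The documents do not support reading this as a threat to the primary conclusion. It merits correction because the ascertainment gap is avoidable and later analysis cannot fill it.

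**What to change.** In 8.4.2.3.4, state that the restricted visit list governs the 4 mL PK draws. Add that in the efficacy study the smear and dried blood spot continue by finger prick at every visit scheduled in 1.3.2. Leave the hemoglobin condition on blood draws unchanged; how it applies to the optional 0.5 mL venipuncture is for the sponsor and the safety oversight bodies to reconcile.

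If the efficacy visits are already complete under this version, say in 9.4.4 how follow-up after a detected pregnancy is analyzed.

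The cost is a sentence or two of text and at most about five extra finger pricks per affected subject, at visits that already exist.

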8.4.2.4 Sponsor's Reporting Responsibilities

Events reported to the sponsor will be promptly evaluated and will be reported as required according to FDA IND safety reporting guidance and regulations. IND safety reports will be sent to other investigators conducting research under the same IND and will be shared with other stakeholders according to applicable agreements.

The sponsor will also submit an IND annual report of the progress of the investigation to the FDA as defined in 21 CFR 312.33.

All UPs will be evaluated by the sponsor, and a summary of the event, and any necessary (corrective/preventative) actions, will be distributed to investigators conducting research under the same IND as may be relevant and appropriate.

8.4.3 Withdrawal Criteria for an Individual Subject

An individual subject will be withdrawn from the study for any of the following:

- An individual subject's decision. (The investigator should attempt to determine the reason for the subject's decision.)
- Non-compliance with study procedures to the extent that it is potentially harmful to the subject or to the integrity of the study data.
- A change in the subject's condition as follows:
 - Loss of the ability to provide informed consent.
 - Withdraws permission to have blood samples or data stored for future research.
- The investigator determines that continued participation in the study would not be in the best interest of the subject.

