6 STUDY INTERVENTION

6.1 STUDY INTERVENTION ADMINISTRATION

6.1.1 Study Intervention Description

The study intervention involves a single administration of CIS43LS or placebo to each subject. All study agent administration will take place at the Kalifabougou study site.

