6.5 CONCOMITANT THERAPY

All concomitant prescription and nonprescription (including over-the-counter, herbal, or traditional) medications taken during study participation will be recorded. For this protocol, a prescription medication is defined as a medication that can be prescribed only by a properly authorized/licensed clinician.

Treatment with the following drugs and procedures will not be permitted unless discussed with and approved by the investigator:

- Live vaccines within 4 weeks of study agent administration.
- Killed vaccine within 2 weeks of study agent administration.
- Immunoglobulins and/or blood products for the duration of the study.
- Receipt of any investigational product or co-enrollment in other clinical studies of investigational products.
- Oral or IV corticosteroids at immunosuppressive doses (i.e., prednisone >10 mg/day) or immunosuppressive drugs for the duration of the study.
- Antimalarials and antibiotics with known antimalarial activity.

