7 STUDY INTERVENTION DISCONTINUATION AND PARTICIPANT DISCONTINUATION/WITHDRAWAL

7.1 DISCONTINUATION OF STUDY INTERVENTION

Study intervention may be discontinued for a protocol-defined group or arm (i.e., pausing), or it may be discontinued for all subjects and enrollment suspended (i.e., halting). Pausing and halting

Abbreviated Title: Anti-malaria MAb in Mali

Version Date: October 13, 2022

are described in sections [8.4.5](#) and [8.4.6](#). Subjects who have already received the study agent at the time of a pause or halt will continue planned follow-up under the protocol.

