9.3 POPULATIONS FOR ANALYSES

The following datasets will be considered in study analyses:

- Intention-to-treat (ITT) analysis dataset will include all subjects that receive assignment and will be analyzed according to the initial randomization assignment.
- Modified intention-to-treat (MITT) analysis dataset will include all randomized subjects that receive the study intervention and will be analyzed according to the initial randomization assignment.
- Per-protocol analysis dataset will include all randomized subjects that receive the study intervention consistent with the initial randomization assignment and complete the scheduled visits, and will be analyzed according to the initial randomization assignment. In cases where subjects receive an intervention other than the one randomly assigned, an as-treated analysis will be additionally performed according to the actual intervention received.

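### Section 8.4.3 withdraws subjects for data-integrity non-compliance without separating before from after the single infusion; after infusion this only ends follow-up and creates avoidable missing outcome data

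*Combined protocol and SAP*

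**What the plan says.** Section 8.4.3 opens with "An individual subject will be withdrawn from the study for any of the following". One listed reason is "Non-compliance with study procedures to the extent that it is potentially harmful to the subject or to the integrity of the study data". The wording is mandatory, the withdrawal is from the study, and no line is drawn between subjects who have and have not been dosed. The bullet has two limbs: harm to the subject and harm to the data. This point concerns the second.

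The other relevant provisions are:

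- **Treatment (6.1.1).** "The study intervention involves a single administration of CIS43LS or placebo to each subject".
- **Analysis sets (9.3, 9.4.4, 9.4.5, 8.4.3.2).** The MITT "analysis dataset will include all randomized subjects that receive the study intervention". For efficacy, "The efficacy analyses will be MITT" and "The primary efficacy analysis will be based on time to the first infection". Safety analysis is also primarily MITT, and every exposed subject must be in the safety dataset.
- **After withdrawal (7.2, 8.4.2.3.2, Table 2).** A dosed subject is encouraged to attend one early termination visit. Unresolved SAEs are followed to outcome, and related SAEs learned of later are still recorded. No further scheduled smears are provided for.
- **Stopping of dosing (7.1).** "Subjects who have already received the study agent at the time of a pause or halt will continue planned follow-up under the protocol". Sections 8.4.5.3 and 8.4.6.3 likewise keep a subject in safety follow-up when agent is not resumed.
- **Replacement (8.4.3.2).** In the efficacy study, only subjects withdrawn before dosing are replaced.

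**The concern.** After day 0 a non-compliant subject has no remaining study treatment to discontinue, so withdrawal can act only on data collection. The subject stays in the MITT set, is not replaced, and in a time-to-first-infection analysis is in effect censored at the last smear. A rule meant to protect the data therefore removes primary-endpoint and safety data that cannot be recovered later.

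The loss may also be related to the outcome. Section 6.5 lists "Antimalarials and antibiotics with known antimalarial activity" among treatments not permitted without the investigator's approval. If unapproved use of this kind were treated as data-threatening non-compliance, a subject who took an antimalarial for a fever could be withdrawn just before a smear would have been positive. The documents do not say that this would happen; it is an example of how the loss could become informative.

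The planned safeguards cover this only in part. Section 9.4.1 treats missing data as missing completely at random when below about 10%. Its missing-not-at-random sensitivity analyses are worded for binary observations, whereas the primary analysis is time-to-event.

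**Working it through.** **Step 1: effect of the rule by stage.**

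- *Between enrollment and day 0.* Enrollment is the first artemether-lumefantrine dose, and the course must be finished before infusion. A subject withdrawn here is undosed, outside MITT and replaced. The data-integrity limb has a clear use at this stage.
- *After infusion.* No agent is left to stop, the subject is in MITT and the safety dataset, and there is no replacement. Scheduled smears, dried blood spots and AE visits end.

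The analysis plan can already accommodate such subjects if they are followed. Section 9.3 has a per-protocol set that requires completed visits, and the primary methods in 9.4.4 allow for interval censoring and so can use irregular visits.

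**Step 2: reproduce the plan's power.** Inputs from 9.2.2: 110 per arm, 10% drop-out, placebo infection rate p0 = 0.40, protective efficacy 0.5 so p1 = 0.20, two-sided alpha 0.025 (z = 2.241). Stated power is 80%.

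Power = Φ{ [ (p0 − p1) − z·√(2·p̄(1 − p̄)/n) ] / √( [p0(1 − p0) + p1(1 − p1)]/n ) }, with p̄ = 0.30.

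At n = 0.9 × 110 = 99: (0.20 − 2.241 × 0.0651)/0.0636 = 0.85, so power = 80.2%. Twenty Table 4 cells checked in this way agree with the stated values to within about half a point. Table 4 is therefore a pooled two-proportion calculation after 10% loss.

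**Step 3: what retention could be worth.** Same formula, 0.40 against 0.20:

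| Total loss | n per arm | Power |
|---|---|---|
| 0% | 110 | 84.6% |
| 5% | 104 | 82.3% |
| 10% (plan) | 99 | 80.2% |
| 12% | 97 | 79.3% |
| 15% | 94 | 77.9% |
| 20% | 88 | 74.8% |

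Within the plan's allowance, all drop-out together costs 84.6 − 80.2 = 4.4 points. This rule accounts for an unknown part of that. The table overstates the cost, because a withdrawn subject still contributes time up to the last smear. At placebo rate 0.5 and protective efficacy 0.5, Table 4 gives 93%, and 15% loss would still leave 91.1%.

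**Step 4: direction of any bias.** The removal shares below are assumptions; the documents give none.

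- *Equal shares, proportion scale.* If a share f of would-be infected subjects is removed undetected in both arms, p′ = p(1 − f)/(1 − pf). At 0.40 against 0.20, f = 5% gives 0.388 and 0.192 (protective efficacy 0.505), and f = 20% gives 0.348 and 0.167 (0.521). The true value is 0.50.
- *Unequal shares, hazard scale.* The hazard ratio is ln(0.8)/ln(0.6) = 0.437, a protective efficacy of 0.563. Multiply the hazard ratio by (1 − f1)/(1 − f0), where f0 is the share removed on placebo and f1 on CIS43LS. With f0 = 15% and f1 = 5%, protective efficacy is 0.512. With f0 = 5% and f1 = 15%, it is 0.609.

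**The case against.** The strongest reply is that the criterion has a threshold, leaves judgement to the investigator, and may seldom be used after infusion. Other provisions handle most non-compliance without withdrawal. Section 7.3 requires contact and rescheduling after a missed visit, and counts a subject as lost only after three consecutive missed visits without contact. Section 8.4.1 classes departures that damage scientific integrity as major deviations, and 8.6.1 and 10.9 require them to be reported. The per-protocol set presupposes that subjects who miss visits otherwise remain in the study. Subjects, clinical staff and study team are blinded, so no mechanism for unequal removal is evident. Section 7.1 concerns stopping dosing for an arm or the whole study, not one subject's conduct.

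Most of this stands as a limit on size. It does not remove the point: 8.4.3 as written still requires withdrawal once its threshold is met, and nothing exempts infused subjects. The deviation provisions show that a suitable alternative already exists.

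Two stronger readings are tempting, and the documents support neither. A reader might infer that the rule acts only on dosed MITT subjects. It also covers subjects before day 0, who are replaceable, and it has a subject-harm limb. A reader might also infer that it removes subjects for malaria-related behaviour. Section 8.4.3 does not say so, 6.5 allows investigator approval, and 8.2.1 provides treatment for symptomatic, smear-positive malaria within the protocol.

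**Conclusion.** The point holds as a limited design issue. For subjects already infused, mandatory withdrawal on data-integrity grounds has no treatment purpose and ends scheduled outcome collection for people who remain in the primary analysis set. It also sits poorly with the protocol's practice of following subjects when dosing is stopped.

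The size cannot be established, because no rate of such withdrawals is given. The only bound from the plan's own figures is about 4.4 points of power for all drop-out within the 10% allowance, at placebo rate 0.4 and protective efficacy 0.5. That allowance does not exclude involuntary withdrawals, so losses under this rule should not automatically be stacked on top of it. A reader might infer from the illustrations in Step 4 that protective efficacy will be biased by about 0.05. That needs removal of 15% against 5% of would-be infections, which nothing in the documents supports. All that can be said is that bias is possible and could go in either direction. The change is a cheap improvement, not a condition for the validity of the trial.

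**What to change.** In 8.4.3, limit the data-integrity limb to subjects not yet infused. Add that after infusion such non-compliance is recorded as a protocol deviation and that scheduled smear, dried-blood-spot and AE visits continue. Leave unchanged the criteria for the subject's own decision, harm to the subject, loss of ability to consent, withdrawn permission for storage, and best interest.

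Keep MITT as the primary analysis and use the existing per-protocol set as the supportive one. Do not add a sensitivity analysis that censors at antimalarial use, since it would reintroduce the outcome-dependent censoring the change is meant to avoid.

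The cost is a short wording change in 8.4.3 with no new analysis. The small downside is that some irregular or protocol-deviating data enter the MITT analysis.
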